3.1.2. Laboratory Data

Safety laboratory tests will be performed as described in the protocol. To determine if there are any clinically significant laboratory abnormalities, the hematological, clinical chemistry (serum) and urinalysis safety tests will be assessed against abnormality criteria. Moreover, GLDH will be summarized to monitor the liver toxicity. Other parameters to be summarized can be found in Section 6.1.2.

Baseline is defined as the last pre-dose measurement.

3.1.3. Vital Signs

Blood pressure (systolic and diastolic), respiratory rate, and pulse rate measurements will be taken at times detailed in the Schedule of Activities given in the protocol. Body temperature may also be collected if clinically indicated.

Baseline is defined as the last pre-dose recording.

3.1.4. Electrocardiograms

Triplicate 12-lead ECGs will be recorded according to the Schedule of Activities in the protocol.

The QT interval, QTcF interval, PR interval, RR interval, QRS complex and heart rate will be recorded at each assessment time.

If not supplied, QTcF interval will be derived using Fridericia's heart rate correction formula: $QTcF = QT / (RR)^{1/3}$ where RR = 60 / heart rate (if not provided)

The average of the triplicate readings will be calculated for each ECG parameter.

Baseline will be defined as the average of the last triplicate ECG measurements collected prior to dosing on Day 1.

3.1.5. Cardiac MRI (or Echocardiogram, if necessary)

Cardiac MRI (or echocardiogram) will be collected at times specified in the Schedule of Activities section of the protocol. The mean absolute and percent change from baseline in

cardiac parameters including LVEF, LV Fractional Shortening (%), LV mass index, will be evaluated and the number (%) of participants with the presence of late gadolinium enhancement will be provided.

Baseline is defined as the last pre-dose measurement.

3.1.6. Other Safety Data

Additional safety data (neurological and physical examination, infusion site reaction and C-SSRS will be collected as described in the protocol and will be listed and/or summarized.

3.2. Secondary Endpoint(s)

3.2.1. Mini-dystrophin expression and distribution

- 1. Change from Baseline in percent normal dystrophin expression level in biceps brachii muscle biopsies at 2 (or 3) and 12 months post-treatment using an LC-MS assay
- 2. Change from Baseline in percent of dystrophin-positive muscle fibers in biceps brachii muscle biopsies at 2 (or 3) and 12 months post-treatment as assessed by immunofluorescence.

3.2.1.1. Mini-dystrophin expression

Dystrophin and mini-dystrophin expression levels will be measured by LC-MS assay. For the LC-MS assay, there are two reportable peptides:

- 1. LEMPSSLMLEVPTHR (LEMP) peptide results will quantify the mini-dystrophin transgene protein levels following treatment with fordadistrogene movaparvovec.
 - No mini-dystrophin transgene protein will be expressed in the tissue samples obtained prior to the administration of fordadistrogene movaparvovec.
- 2. LLQVAVEDR (LLQV) peptide results will quantify the total dystrophin protein including both full-length, endogenous dystrophin protein and the mini-dystrophin transgene protein.

Revertant endogenous fibers usually exist due to a mechanism that restores the reading frame (Klein et al., 1992¹). Dystrophin levels from revertant fibers may be measurable by LC-MS assay. Baseline is defined as the endogenous dystrophin levels reflected in the tissue sample collected prior to the administration of fordadistrogene movaparvovec.

3.2.1.2. Mini-dystrophin distribution

Muscle fibers expressing both endogenous dystrophin protein and mini-dystrophin transgene protein will be identified by positive staining. Percentage of positive muscle fibers will be calculated for each muscle biopsy.

Dystrophin distribution will be evaluated by immunofluorescent staining using two antibodies.

1. DYSB antibody that recognizes both endogenous dystrophin protein and minidystrophin transgene protein from the pre-dose tissue biopsy for the endogenous dystrophin antibody.

For the baseline assessment, the distribution of the fiber MSD for each individual fiber will be evaluated for each participant to assess the expression level of total dystrophin protein. Baseline will be derived from the fiber MSD for each individual fiber in the tissue biopsies that were obtained prior to the administration of fordadistrogene movaparvovec.

2. Mini-dystrophin specific antibody that only recognizes the mini-dystrophin transgene protein

No mini-dystrophin transgene protein fibers will be contained in the tissue samples obtained prior to the administration of fordadistrogene movaparvovec.

The positive threshold value for the mini-dystrophin specific antibody represents a pooled average MFI value from 19 ambulatory baseline, pretreatment biopsies.

[figure not shown]
For the determination of percent of positive muscle fibers and the derivation of the baseline value, refer to Section 6.2.2 for details.

[figure not shown]

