For each participant, the individual baseline fiber MSD method will be used to determine the threshold for positive fibers to better characterize the individual change from baseline. The distribution of the individual fiber MSD data will be examined and plotted. The 95th percentile of the baseline fiber MSD distribution for each slide obtained prior to dosing will be computed. The maximum of the 95th percentiles obtained from the baseline distribution(s) will be used as the threshold for positive fibers. This individual threshold of staining density will be established for each participant such that at least 95% of fibers have a staining density below the threshold for each slide analyzed at baseline.

For the newly developed mini-DYS/Laminin Image Analysis assay, a global threshold for calculating the percentage of mini-dystrophin positive fibers will be established based on all baseline samples from the 19 ambulatory participants. The quantification of the immunofluorescence intensity level (MSD) associated with the individual muscle fibers will be used to calculate the 99th percentile of the overall fiber MSD distribution. The

[figure not shown]
corresponding fiber MSD threshold value will be determined. Any muscle fiber with an MSD value above this calculated threshold value will be considered as a positive fiber.

[figure not shown]
At each scheduled visit of muscle biopsy, the average of the percent of positive fibers obtained in each slide will be computed. This percent of positive fibers will be summarized by dose cohort and ambulatory status at baseline. Key fiber MSD distribution statistics including the mean and the median will be summarized. In addition, non-parametric Wilcoxon test will be used to examine the change in fiber MSD distributions.

[figure not shown]

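### SAP 3.2.1.2 and 6.2.2 give different positivity thresholds for the mini-dystrophin antibody, and percent change from baseline is ordered for two endpoints whose pre-dose value is nil or background

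*SAP*

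**What the plan says.** **Threshold.** SAP 3.2.1.2, on the mini-dystrophin specific antibody, says: "The positive threshold value for the mini-dystrophin specific antibody represents a pooled average MFI value from 19 ambulatory baseline, pretreatment biopsies". It adds: "For the determination of percent of positive muscle fibers and the derivation of the baseline value, refer to Section 6.2.2 for details". Section 6.2.2 sets one global threshold from the baseline samples of the 19 ambulatory participants. It names its input as "The quantification of the immunofluorescence intensity level (MSD) associated with the individual muscle fibers" and says that this input "will be used to calculate the 99th percentile of the overall fiber MSD distribution". A fibre above that value counts as positive.

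**Pre-dose values.** For the LEMP peptide, SAP 3.2.1.1 says: "No mini-dystrophin transgene protein will be expressed in the tissue samples obtained prior to the administration of fordadistrogene movaparvovec". For the mini-dystrophin antibody, 3.2.1.2 says: "No mini-dystrophin transgene protein fibers will be contained in the tissue samples obtained prior to the administration of fordadistrogene movaparvovec". For the LLQV peptide (total dystrophin), 3.2.1.1 allows that revertant dystrophin may be measurable before dosing.

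**Summaries.** Sections 6.2.1 and 6.2.2 order raw values, change and percent change from baseline, in tables and box plots, for all three LC-MS endpoints and both immunofluorescence endpoints. Section 5.3.3 imputes 0.5*LLOQ for low LC-MS results but is worded for treatment-induced mini-dystrophin levels. Section 6.2.1 simply refers to it.

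**DYSB.** Section 6.2.2 sets each participant's threshold at the highest of the 95th percentiles of his own baseline slides, so that "at least 95% of fibers have a staining density below the threshold for each slide analyzed at baseline". At each biopsy visit "the average of the percent of positive fibers obtained in each slide will be computed".

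**The concern.** An average and a 99th percentile are different cut-offs. The SAP's estimand table (2.1) includes change from baseline in percent positive fibres on this antibody, and SAP 5.1 and 6.2 plan 95% bootstrap intervals for the secondary endpoints. All of these move with the threshold. The measure is also named differently: MFI in 3.2.1.2 and MSD in 6.2.2, and the abbreviation list carries them as separate terms.

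Percent change needs a baseline that means something. Where the plan itself expects no transgene product before dosing, the denominator is zero, an imputed constant or assay background, so the size of the percentage reflects the assay limit or the threshold rule as well as the treatment. With cohorts of 3, 16 and 3 (SAP 2.5), one near-zero denominator could dominate a mean.

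**Working it through.** The documents give no LLOQ, fibre counts, slide numbers or stain distribution. Those inputs below are assumptions.

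**1. The plan's own figure.** SAP 6.2.2 says that at least 95% of fibres on each baseline slide lie below the DYSB threshold. This reproduces: in simulation of the rule (lognormal stain density, 1 to 3 slides) no baseline slide exceeded 5.00% positive.

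**2. Share of pooled baseline fibres positive on the mini-dystrophin antibody.**
- 99th percentile (6.2.2): 1%, whatever the distribution.
- Literal average (3.2.1.2), lognormal: share = 1 - Phi(s/2), s = sqrt(ln(1 + CV^2)). CV 0.3, 0.5, 1, 2 gives 44.2%, 40.7%, 33.9%, 26.3%.
- Symmetric: 50%. Left-skewed Beta(5,2), Beta(8,2), Beta(5,1): 54.8%, 56.4%, 59.8%.

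**3. Effect on change from baseline.** Assume lognormal fibres with log-SD 0.3 that all shift upward after dosing. The baseline is 1.0% under the percentile and 44.0% under the average.

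| Log shift | 99th percentile | Average |
|---|---|---|
| 0.6 | 37.2 - 1.0 = +36.2 points | 96.8 - 44.0 = +52.8 points |
| 1.0 | 84.3 - 1.0 = +83.3 points | 99.9 - 44.0 = +55.9 points |

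The rule matters, and the direction of the difference is not fixed.

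**4. LEMP.** In LLOQ units, percent change = 100 x (k - b)/b for a post-dose value k and baseline b.
- b = 0: undefined.
- b = 0.5: k = 2, 10, 50 gives +300%, +1,900%, +9,900%.
- For a post-dose level of 100 fmol/mg, an LLOQ of 2 gives (100 - 1)/1 = +9,900% and an LLOQ of 20 gives (100 - 10)/10 = +900%. Absolute change goes only from 99 to 90.
- Choosing b = 0 or b = 0.5 also moves the absolute change by half an LLOQ: 2.0 or 1.5 at k = 2, and 10.0 or 9.5 at k = 10.

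**5. Mini-dystrophin antibody, 6.2.2 rule, post-dose 50%.** Percent change = 100 x (50 - b)/b.
- b = 1%: +4,900%. b = 2%: +2,400%. b = 0%: undefined.
- Chance of a 0% baseline at a true 1% rate is 0.99^n: 13.4% for 200 fibres and 0.7% for 500. This assumes the same background in every biopsy.
- With between-participant log-SD of 0.3 to 0.5, simulated baselines ran from about 0% up to 3% to 12%, and 1% to 67% of participants read exactly 0%.
- The 1% is a pooled figure for the 19 ambulatory participants. It is not assured for the three non-ambulatory participants, whose samples do not enter the threshold.

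**6. DYSB.** The slide that sets the threshold has 5% of fibres above it and the others 0% to 5%, so the mean of k slides lies between 5/k% and 5%, and is exactly 5% with one slide. Simulation-average baselines for two or three slides were 2.2% to 4.7%. At a post-dose value of 50%, b = 5, 4.7 and 2.2 gives +900%, +964% and +2,173%, while absolute change is +45.0, +45.3 and +47.8 points.

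**7. LLQV.** For a post-dose value of 10 x LLOQ, a baseline at the LLOQ gives +900%. A baseline just below it, if imputed as 0.5*LLOQ, gives +1,900%. Absolute change is 9.0 or 9.5 x LLOQ.

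**The case against.** The strongest reply is that the threshold conflict is editorial. Section 3.2.1.2 sends the reader to 6.2.2, which gives a complete rule, and 6.2.2 itself calls MSD an intensity level, so MFI may be loose naming. This largely stands: the average-based figures describe a rule unlikely to be run. The sentence is still wrong where the endpoint is defined. An average of per-biopsy 99th percentiles would reconcile the sections, but neither says that, and it would generally differ from the pooled 99th percentile.

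On percent change, the reply is that raw values, absolute change and individual plots are already planned, SAP 5.1 has no formal hypothesis testing, and the individual DYSB threshold is deliberate. That also stands and limits the point to displays. Three stronger inferences are not supported:

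- **That participants cannot be compared on LEMP percent change.** If every baseline is 0.5*LLOQ with a common LLOQ, percent change = 200 x (post/LLOQ) - 100. It is a linear rescaling that still ranks participants and carries the treatment effect. It is redundant and its size is set by the LLOQ. The same holds for DYSB if everyone has one baseline slide.
- **That percent change fails for all five endpoints.** LLQV may have a measurable endogenous baseline. Only participants below the LLOQ are affected, and whether 5.3.3 reaches their pre-dose values is uncertain from its wording.
- **That DYSB percent change swings threefold.** This needs three slides with the other two at exactly 0%, giving a 1.67% baseline and +2,900% against +900%. It is an extreme bound; average simulated baselines were 2.2% to 4.7%.

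**Conclusion.** The concern holds, at minor severity. The two sections state different thresholds for the same antibody, most likely through an outdated or loose sentence in 3.2.1.2. A reader might infer that the endpoint has no usable definition; the cross-reference to 6.2.2 argues against that. A reader might equally infer that no estimand is touched, which is true only of the percent-change displays. The threshold feeds the antibody's percent positive and its change from baseline, and the unstated handling of pre-dose LEMP values feeds LEMP absolute change, by half an LLOQ.

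Percent change is undefined or a rescaling by the LLOQ for LEMP, and a division by false-positive background for the mini-dystrophin antibody. For DYSB and for LLQV baselines below the LLOQ, it needs a caveat. The 1% pooled background and the 5% DYSB ceiling follow from the SAP's rules; the quarter-to-60% range and the other illustrations rest on the assumed inputs. The primary endpoints are untouched.

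**What to change.** 1. In SAP 3.2.1.2, replace the pooled-average sentence with the 6.2.2 rule and use one name, MFI or MSD, throughout. If something else was meant, such as an average of per-biopsy percentiles, say so in both sections.
2. In 6.2.1 and 6.2.2, drop percent change from tables and box plots for LEMP and the mini-dystrophin antibody. Keep raw values and absolute change.
3. In 5.3.3, state whether pre-dose values below the LLOQ are imputed as 0.5*LLOQ.
4. Footnote DYSB percent change as driven by the threshold rule (baseline at most 5% by construction, exactly 5% with one slide), and any LLQV percent change from a baseline below the LLOQ as LLOQ-driven.

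The cost is a few sentences of SAP text and some descriptive columns and plots. No data collection or estimand definition changes.

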3.2.2. Long-term safety

Incidence, severity and causal relationship of TEAEs and clinically significant safety findings, as described for the primary endpoints (above) through 5 years post-treatment.

Baseline is defined the same as those described in Section 3.1.

3.4. Baseline Variables

Participants' demographics and medical history will be collected at screening visit.

The ambulatory status upon enrollment, ie, whether the participant is able to walk unassisted and without braces for at least 10 meters, is considered as a stratification factor. All analyses will be conducted by the ambulatory status at baseline unless otherwise specified.

Screening age (years) covariate is defined as the participant's age on the day of the Screening visit. Age at dosing (years) covariate is defined as the participant's age on the day of the administration of fordadistrogene movaparvovec (Dosing visit).

The following baseline variables will be summarized:

- Demographic characteristics including age, race, and ethnicity, where age is calculated as age in years at the Screening visit and at the Dosing visit.
- Physical measurements at Baseline include height (cm) and weight (kg) where Baseline is defined as the last non-missing pre-dose measurement. For non-ambulatory participants, the height may represent the estimated height derived from the participant's ulnar length per protocol's instructions if the participant is unable to stand safely.
- Background glucocorticoid regimen (including specific medication and daily dose in mg/kg, and duration of current glucocorticoid regimen use) at the Screening visit, and age at initiation of any glucocorticoid use (years).
- General medical history, including diseases or syndromes that are ongoing ('present')
 at, or stopped ('past') before, Screening. MedDRA will be used to code the
 disease/syndrome.

4. ANALYSIS SETS (POPULATIONS FOR ANALYSIS)

Data for all participants will be assessed to determine if the participants meet the criteria for inclusion in each analysis population prior to releasing the database.

For purposes of analysis, the following populations are defined:

Population	Description	
Enrolled	All subjects who sign the informed consent document.	
FAS	All enrolled participants who receive fordadistrogene	
	movaparvovec. Analyses will be performed on the FAS	
	population unless otherwise specified.	
Safety	All enrolled participants who receive fordadistrogene	
	movaparvovec. Participants will be analyzed according to	
	intervention they actually received.	
Pharmacodynamic	All participants in the FAS who have baseline and at least	
Analysis Set	one post-dose mini-dystrophin parameters of interest reported.	

Population	Description
Ambulatory	All participants in the FAS who meet the study eligibility
	criteria for ambulatory status at enrollment: able to walk 10
	meters unassisted and rise from floor within seven seconds.
Non-ambulatory	All participants in the FAS who meet the study eligibility
	criteria for non-ambulatory status at enrollment: unable to walk
	10 meters unassisted.
Low dose cohort	All participants in the FAS who receive 1E14 vg/kg per the
	ITR-based method.
High dose cohort	All participants in the FAS who receive 3E14 vg/kg per the
	ITR-based method or 2E14 vg/kg per the TG-based titer
	method.
CCI	
Non-sirolimus cohort	All participants in the FAS who do not receive sirolimus within
	2 weeks before and after fordadistrogene movaparvovec
	infusion.
Regardless of adherence to	All participants in the FAS, regardless of adherence to
glucocorticoid regimen	background or protocol-mandated glucocorticoid regimens.

The term "ambulatory status at baseline" will be used to describe the stratification factor (ambulatory versus non-ambulatory) used to partition the study participants and report the corresponding group results. The term "overall" will be used to refer to all participants in the FAS.

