3.2. Planned Number of Subjects

Depending on availability of investigational product, up to 22 subjects, including up to 19 ambulatory subjects and 3 non-ambulatory subjects, including those participating in the sirolimus cohort, are planned to participate in up to 5 centers in the United States (US).

Subjects who are withdrawn for reasons other than safety may be replaced at the discretion of the sponsor.

It is anticipated that approximately 40% of the general population may have detectable NAb to AAV9⁵³ which would preclude participation in this trial (see Exclusion Criteria). Thus, in consideration of this criterion and the other eligibility criteria, approximately 37 subjects may need to be screened in order to meet the overall enrollment target. In light of this screen failure rate, efforts will be made to minimize subject burden by obtaining the NAb results prior to conducting the other Screening procedures, when feasible, while also balancing the timing of the Screening visits with the staggered enrollment. Such efforts will require close communication between the site staff and sponsor study team.

^{*}Dose-level determined by inverted terminal repeat (ITR)-titer based assay, but PF-06939926 3E+14 vg/kg using the ITR- based titer assay is approximately equivalent to PF-06939926 2E+14 vg/kg under the transgene (TG)-based titer assay.

[^]Number of biopsies may be reduced or eliminated for the non-ambulatory subjects as per sponsor discretion.

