6.2.1. Mini-dystrophin/Dystrophin Expression by LC-MS

Endpoints:

- Mini-dystrophin levels, expressed as fmol/mg of total protein, measured by LC-MS assay, LEMPSSLMLEVPTHR (LEMP) peptide
- Total dystrophin levels, expressed as fmol/mg of total protein, measured by LC-MS assay, LLQVAVEDR (LLQV) peptide
- Total dystrophin levels, expressed as percent normal, measured by LC-MS assay, LLQVAVEDR (LLQV) peptide

The analyses listed below will be performed for each of the 3 endpoints. The method for handling results below the LLOQ is described in Section 5.3.3. The analyses will be performed using the Pharmacodynamic Analysis Set. Presentations will include:

- Raw values, change from baseline and % change from baseline will be summarized descriptively by dose cohort, ambulatory status at baseline, and study visit.
- A boxplot (for cohort(s) with over 3 participants, data points display only for cohort with ≤3 participants) presenting the distribution of the change from baseline against study visit. A similar plot will also be generated for raw values and % change from baseline.
- An individual plot presenting raw levels against study visit, paged by dose cohort and ambulatory status at baseline. A similar plot will also be generated for the change from baseline.

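### The single Pharmacodynamic Analysis Set demands a measured baseline even for raw post-dose LEMP and IF mini-dys values, which can be obtained without one

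*SAP*

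**What the plan says.** **Analysis set.** SAP Section 4 defines the set in two conditions: "All participants in the FAS who have baseline and at least" followed by "one post-dose mini-dystrophin parameters of interest reported". Section 6.2.1 applies it to the three LC-MS endpoints ("The analyses will be performed using the Pharmacodynamic Analysis Set"), and Section 6.2.2 does the same for the two immunofluorescence endpoints. In both sections the set governs raw values, change and % change from baseline, boxplots and individual plots. The visible text has no exception for a missing baseline biopsy.

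**Transgene-specific endpoints.** For LC-MS, SAP 3.2.1.1 states: "No mini-dystrophin transgene protein will be expressed in the tissue samples obtained prior to the administration of fordadistrogene movaparvovec". For the mini-dystrophin-specific antibody, 3.2.1.2 states: "No mini-dystrophin transgene protein fibers will be contained in the tissue samples obtained prior to the administration of fordadistrogene movaparvovec". Section 6.2.2 sets the IF mini-dys positivity threshold globally, "based on all baseline samples from the 19 ambulatory participants". For DYSB, by contrast, it takes the threshold from each participant's own baseline slides.

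**Biopsies.** The footnote to the study schematic in Protocol 3.2 reads: "Number of biopsies may be reduced or eliminated for the non-ambulatory subjects as per sponsor discretion". Protocol 7.6 repeats the option to take fewer biopsies in these subjects, with the sponsor telling sites which timepoints apply. Protocol 1.4.2 presents the baseline biopsy as a possibility, and 6.2 makes it conditional on one being taken.

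**The concern.** The measured-baseline requirement suits endpoints that include endogenous dystrophin. LLQV counts endogenous and transgene protein together, and DYSB percent positive cannot be computed without the participant's own baseline threshold. Neither reason applies to a raw post-dose LEMP level or a raw post-dose IF mini-dys percentage. Each is direct evidence of transduction as it stands.

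The SAP nevertheless ties these raw values to the same set. A non-ambulatory participant with a post-dose biopsy but no baseline biopsy, a pattern the protocol permits, would be missing from the summaries and plots of both. He would still belong to the secondary estimand population in SAP 2.3, which is everyone eligible who was infused. What is at stake is descriptive expression evidence in a cohort of three.

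**Working it through.** **1. Cohort sizes (SAP 2.5).** Ambulatory low dose 3, ambulatory high dose 16, non-ambulatory high dose 3. The sum is 3 + 16 + 3 = 22, which reproduces the SAP's total. The one sirolimus participant is counted within the non-ambulatory 3. The high-dose cohort is 16 + 3 = 19.

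**2. Does each endpoint need the participant's own baseline to give a raw post-dose value?**

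| Endpoint | Own baseline needed for raw post-dose value? | Reason |
|---|---|---|
| LEMP, fmol/mg | No | Transgene-specific level, measured directly |
| IF mini-dys, % positive | No | Scored against a pooled threshold |
| LLQV, fmol/mg | To interpret it | Includes endogenous dystrophin |
| LLQV, % normal | To interpret it | Includes endogenous dystrophin |
| IF DYSB, % positive | Yes, to compute it | Threshold is the participant's own baseline percentile |

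SAP 3.2.1.2 calls the IF mini-dys threshold a pooled average, while 6.2.2 makes it a 99th percentile. On either description it comes from ambulatory baseline samples, so a non-ambulatory participant's own baseline plays no part in scoring his post-dose slide.

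**3. Membership of the set.** Let k be the number of non-ambulatory participants without a baseline result. Assume that all 3 have a post-dose result and that the 19 ambulatory participants all qualify. Under the current rule, non-ambulatory n = 3 − k, high-dose n = 19 − k and overall n = 22 − k.

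| k | Non-ambulatory n | High-dose n | Overall n | Non-ambulatory lost (k/3) | All lost (k/22) |
|---|---|---|---|---|---|
| 0 | 3 | 19 | 22 | 0% | 0% |
| 1 | 2 | 18 | 21 | 33.3% | 4.5% |
| 2 | 1 | 17 | 20 | 66.7% | 9.1% |
| 3 | 0 | 16 | 19 | 100% | 13.6% |

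If only a post-dose result is required for the raw LEMP and IF mini-dys summaries, these n stay at 3, 19 and 22 for every k.

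**4. Can the gap be closed by imputing a nil baseline?** No, for three reasons.
- The 0.5 × LLOQ rule in SAP 5.3.3 covers the LC-MS peptides only. IF mini-dys has no corresponding convention.
- With a 99th-percentile cut, about 100% − 99% = 1% of the pooled baseline fibers are positive by construction. A measured IF baseline is therefore not zero, even though the biology says nil.
- Sections 6.2.1 and 6.2.2 also ask for % change. That is undefined from a baseline of 0, and from 0.5 × LLOQ it depends on the assay limit.

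**5. Second exclusion.** SAP 6.2 summarises only tissue that has results from every planned assay. A participant without a baseline has no DYSB percent-positive result, so this rule could exclude the same tissue even after Section 4 is relaxed. Both places need attention.

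**The case against.** The strongest objection is that the loss may never occur. Protocol 7.6 makes a baseline biopsy the default for all subjects unless the sponsor instructs otherwise. The Schedule of Activities and Protocol 6.2 accept an adequate biopsy taken outside the study in its place. Harm needs one particular pattern: baseline dropped, post-dose biopsy kept, and no outside sample. If every biopsy was dropped, there is no post-dose result to lose. This stands, and it is why the point is conditional.

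It can also be said that requiring a measured baseline is conventional, because the estimand is change from baseline. A non-ambulatory participant's own baseline is also the only within-person check that a threshold derived from ambulatory tissue carries over to more advanced disease. Both points stand for the change analyses. They do not justify withholding the raw post-dose value, which the SAP separately asks to be summarised.

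Three stronger readings are tempting but unsupported:
- **That non-ambulatory baselines were not taken, because the SAP mentions 19 ambulatory baseline samples.** That wording only sets the IF mini-dys threshold. SAP 3.2.1.1, 3.2.1.2 and 6.2.2 otherwise define baseline without regard to ambulatory status.
- **That the only expression evidence in the smallest cohort would go.** The ambulatory low-dose cohort also has 3 participants, and if k is 1 or 2 the remaining non-ambulatory participants still contribute.
- **That data would be discarded.** The set governs summaries and plots. Nothing in the visible text prevents a listing or narrative.

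**Conclusion.** The point holds as a minor, conditional flaw. The SAP attaches a measured-baseline requirement to raw summaries of two endpoints that do not need it, and the protocol permits the biopsy pattern in which the requirement would bite. The possible loss runs from none to all 3 non-ambulatory participants, or from 0% to 13.6% of the 22 treated.

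This rests on k, which the documents do not state, on all 3 having a post-dose result, and on the ambulatory participants being unaffected. The reference to 19 ambulatory baseline biopsies in SAP 3.2.1.2 suggests that last assumption is right. The primary safety analyses are untouched, and the study has no formal hypothesis test that could be affected. The sponsor knows k and can settle the matter before database release.

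**What to change.** 1. **SAP Section 4.** For raw post-dose values of LEMP and IF mini-dys, use FAS participants with at least one post-dose result for that endpoint, and flag those without a baseline biopsy in tables and plots.
2. **Keep the measured-baseline requirement** for change and % change from baseline on every endpoint, and for all LLQV and DYSB analyses. Do not impute a nil baseline.
3. **SAP Section 6.2.** State that a DYSB percent-positive result missing only because there is no baseline does not exclude the tissue from the raw LEMP and IF mini-dys summaries.
4. **SAP Sections 6.2.1 and 6.2.2.** Point the raw-value presentations of these two endpoints to the relaxed set.

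The cost is a few sentences, with no new procedures or data. Raw and change summaries may then have different n, so each should show its own. In flagged participants the ambulatory-derived IF threshold has no within-person check, and the flag should say so. If k is 0, the results do not change.
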